3.2. Description and justification of the study population

3.2.1. Study population

This retrospective cohort study focuses on the AF population as described in

[figure not shown]

Figure 1, in Appendix 2.

The inclusion criteria for the AF population are:

- Patients with at least one hospital stay with a principal (PD), related (RD) or associated (AD) diagnosis of code I48 (Atrial fibrillation of the International Classification of Disease 10th version, ICD-10) or with an active Long-Term Disease (LTD) at the index date or during the year with ICD-10 code I48;

OR

- Patients who are new users of OACs for the AF treatment with or without AF diagnosis (PMSI-MSO or LTD), identifying with a validated and published algorithm with a high specificity (c-index 0,93), using a predictive model developed in the NACORA study (14,16). The algorithm for identifying patients exposed to OAC indicated for AF is based on the presence of at least one reimbursement of an OAC (VKA, apixaban, rivaroxaban or dabigatran), without use of the same OAC in the 24 months prior to the first reimbursement date. This algorithm considers reimbursement data for the 6 weeks prior to the first OAC reimbursement to distinguish patients treated for AF from those treated for deep venous thrombosis (DVT) or pulmonary embolism (PE). This algorithm includes data on age, gender, use of treatments as use of beta-blockers, antiarrhythmics, antiplatelets, antihypertensive drug, holter/echocardiography procedures, cardiologist prescriber, D-dimer blood test reimbursement.

The exclusion criteria for the AF population correspond to those applied in the NACORA and NAXOS studies and are:

- Patients with at least one hospital stays with an ICD-10 code in PD, RD or AD for associated valve disease, ICD-10 codes I05 to I09, I34 and I39, or valve surgery;
- Patients treated with an OAC for another indication than AF:
 - o Patients who are new users of OACs for the treatment of pulmonary embolism (PE, ICD-10 code I26), or deep vein thrombosis (DVT, ICD codes I80 to I82);
 - o Patients who are new users of OAC, not indicated for AF, PE and DVT, having in the six weeks preceding the first reimbursement of OAC, an orthopedic procedure (osteoarticular or muscular) of the lower limb (including hip/knee replacement) as corresponding to the indication of primary prevention of venous thromboembolic events (root of the Diagnosis Related Group , DRG D02)

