The following table summarizes the criteria for selecting patients from the AF population in the SNDS data.

Cohort	Inclusion criteria	Exclusion criteria
AF Population	
 o Identified patients with AF aged 18 years and older at diagnosis of AF 	
 o - Beneficiaries who are insufficiently identifiable or for whom there are technical

		
constraints in SNDS [fictive pseudoNIR (patient identifier), twins];
 
 ○ - Beneficiaries affiliated to a settlement institution from the oversea French department Mayotte; ○ History of valvular pathology and contraindications to OAC treatment.
--	--	---

Note: Other exclusion criteria will be discussed together with the Scientific Committee

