Then, a logistic model included 14 independent covariables will be applied on unclassified patients to identify AF outpatients. The model will include following covariables: age, gender, use of treatments as use of beta-blockers, antiarrhythmics, antihypertensive drug, holter/echocardiography procedures, cardiologist prescriber, D-dimer blood test reimbursement and presence of hospitalization for arterial thromboembolic event.

Finally, for each unclassified patient, those with a predicted probability above the cut-off value providing specificity of 95% (sensitivity: 63%), will be assumed to be AF outpatients.

9.2.3.2 *Exclusion Criteria*

Patients will be excluded from the study if they meet any exclusion criteria:

- Patients with at least one hospital stay with an ICD-10 code in PD, RD or AD for associated valve disease, ICD-10 codes I05 to I09, I34 and I39, or valve surgery;
- Standard SNDS exclusion criteria (e.g. unicity of identifier not guaranteed, twins, aberrant demographic data, beneficiaries from Mayotte overseas French territory).

[figure not shown]

Figure 2. AF study population according to inclusion and non-inclusion criteria

9.2.3.3 *Populations*

Two populations of AF patients will be considered for analyses according to study objectives:

9.2.3.3.1 *Prevalent AF population*

Prevalent AF patients will be defined as patients diagnosed with AF during the historical period.

Prevalent AF population will be considered for the following analysis:

- To estimate the annual prevalence of patients with non-valvular AF, exposed and unexposed to OAC (objective 4).

9.2.3.3.2 *Incident AF population*

Incident AF patients will be defined as patients newly diagnosed with AF (i.e. no AF diagnostic during the historical period) from January 1st, 2016 to December 31st, 2019 (inclusion period), and to December 31st (2020 for sensitivity analyses).

For incident AF population, two datasets of incident AF patients will be considered for the following analyses:

- For longitudinal analyses: objectives 1, 2, 3 and 7 (cf. 8. Objectives)

Inclusion of patients with:

- An AF newly diagnosed during inclusion period

AND

- No reported events of interest (stroke, major bleeding, and death) within 30 days before index date (i.e. for patients for whom the date of inclusion is not the date of the first dispensation of OA) (cf. 9.2.3.1. Inclusion Criteria)

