D-dimer blood test	
Binary variable (Yes / No)
 
Equals to “Yes” if the patient has reimbursements for at least one D-dimer blood test during the 6 weeks preceding the first date of OAC delivery

	
NABM codes: 1021, 1022.
 
Equals to "No" in other cases

Hospitalization for arterial thromboembolic event	
Binary variable (Yes / No)
 
Equals to "Yes" if the patient is hospitalized at least once with any discharge diagnosis (i.e., principal, related or associated diagnosis) of arterial thromboembolic event (ischemic stroke or transient ischemic attack or systemic arterial embolism) during the 6 weeks preceding the first date of OAC delivery
 
ICD-10 codes: I63 (ischemic stroke) except I63.6 (cerebral infarction due to cerebral venous thrombosis, non-pyogenic), G45 (transient ischemic attack), I74, N28, D73.5, K76.3 (systemic arterial embolism).
 
Equals to "No" in other cases

Then, all the variables representing the exclusion criteria will be derived for each AF patients included after the inclusion criteria and the application of the algorithm ([Table IV](#)).

Table IV. Derived variable for the selection of the population – Exclusion criteria

Variable	Definition
Valvular pathology	
Binary variable (Yes/No)
 
Equals to "Yes" if the patient is hospitalized at least once with any discharge diagnosis (i.e., principal, related or associated diagnosis) of valve disease or valve surgery, during historical or inclusion period
 
ICD-10 codes: I05.x, I06.x, I07.x, I08.x, I09.x, I34.x, I39.x
 
CCAM codes (valve surgery): DBAF003, DBAF002, DBAF005, DBAF004, DBAF001, DBPA002, DBPA004, DBPA005, DBPA006, DBPA007, DBMA008, DBMA012, DBMA003, DBMA002, DBMA011, DBKA004, DBKA008, DBKA007, DBKA012, DBKA010, DBKA005, DBKA002, DBKA006, DBKA003, DBKA001, DBKA011, DBKA009, DBMA007, DBMA013, DBMA005, DBMA009, DBMA010, DBMA006, DBMA001, DBMA015, DBMA004, DBLF009, DBLF001, DBLA004, DBBF198, DBSF001, DBEA001.
 
Equals to "No" in other cases

Standard SNDS exclusion criteria	
Binary variable (Yes / No)
 
See Data Management Plan in section Error! Reference source not found.

Moreover, all the variables used to define the sub-populations will be derived for each patient selected in the study population ([Table V](#)).

Table V. Derived variables for the selection of the populations – Sub-populations

Variable	Definition

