Contraindications to OAC	
Binary variable (Yes/No)
 
Equals to “Yes” if the patient presents at least one contraindication to OAC among the followings:
 
 ● End-stage renal disease on dialysis ● Diseases of the blood and blood-forming organs ● Certain disorders involving the immune mechanism ● Recent history of acute bleeding gastric or duodenal ulcer ● Hepatic cirrhosis or fibrosis or liver failure 
Equals to “No” in other cases.

Chronic renal disease (for contraindications to OAC)	
Binary variable (Yes / No)
 
Equals to “Yes” if the patient meets any criterion below on or in the 2 years prior to the index date:
 
 – A main or related discharge diagnosis of renal transplantation 
ICD-10 code: Z94.0
 
OR

- A renal transplantation surgery
CCAM: JAEA003, HNEA002
 OR
- Is hospitalized at least once with any diagnosis (i.e., main, related or associated diagnosis) of chronic renal disease
ICD-10 codes: N18.x
 OR
- Is covered by the LTD status for chronic renal disease at least one day
ICD-10 codes: N18.x
 OR
- Has received ≥ 19 hemodialysis sessions in inpatient or outpatient settings
CCAM codes : JVJF004, JVJF008, JVRP004
PRS codes : 2121, 2122, 2123, 2126, 2129, 2131, 2132, 2134, 2135, 2136, 2139, 2147, 2334
GHM codes : 11K021, 11K022, 11K023, 11K024, 11K02J, 28Z03Z, 28Z04Z
 OR
- Has received ≥ 1 peritoneal dialysis session in inpatient or outpatient settings
CCAM codes: JVJB001, JVRP007, JVRP008, YYYY007
PRS codes : 2124, 2125, 2127, 2128, 2137, 2138, 2140, 2142, 2143, 2144, 2145, 2146
GHM codes : 28Z01Z, 28Z02Z

Equals to "No" in other cases.

Chronic renal disease requiring dialysis (for contraindications to OAC)	Binary variable (Yes / No) Equals to "Yes" if the patient meets any criterion below on or in the 2 years prior to the index date: 
 - Has the value "Yes" for the variable Chronic renal disease AND - Has at one reimbursement for a dialysis session performed at hospital or in outpatient settings CCAM codes: JVJB001, JVJF004, JVJF008, JVRP004, JVRP007, JVRP008, YYYY007
--	---

	
PRS codes : 2121, 2122, 2123, 2124, 2125, 2126, 2127, 2128, 2129, 2131, 2132, 2133, 2134, 2135, 2136, 2137, 2138, 2139, 2140, 2142, 2143, 2144, 2145, 2146, 2147, 2334
 
GHM codes : 28Z01Z, 28Z02Z, 28Z03Z, 28Z04Z, 11K021, 11K022, 11K023, 11K024, 11K025
 
Equals to “No” in other cases

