9.7.4.2 Comparison of the incidence of stroke, major bleeding, death

Analyses will be performed independently for each event of interest stroke, major bleeding and death.

Survival analysis will be performed to compare incidence rate (stroke, major bleeding or death) in AF incident patients exposed and unexposed to OAC therapy **excluding those with a reported outcomes of interest up to 30 days prior index date**, using a Cox regression model. The Cox regressions models will consider the first event of interest occurring in AF incident patients exposed and unexposed to OAC. OAC exposure will be considered as time-dependent variable and the models will be adjusted for covariates defined below. By applying the OAC exposure variable as a time dependent variable, estimates of Hazard Ratio will account for switches and discontinuations. Time-dependent exposure Cox proportional hazards models will be used to estimate:

- The Crude hazard ratio (i.e. the incidence rate ratio), and therefore the risk of each outcome at any point during the follow-up since index date
- The adjusted hazard ratio on potential confounders including patient:
 - Time-fixed confounders: sex, age (<80, 80-90, >90 years old), prescriber's specialty at initiation of OAC, having malnutrition (yes/no), risk of falls (yes/no), morbid obesity (yes/no), history of stroke (yes/no), history of major bleeding (yes/no), at least one visit to a nursing home (yes/no), history of dementia (yes/no), concomitant treatments (e.g. receiving at least one antiplatelet drugs (yes/no), other anticoagulant drugs (yes/no), etc. - cf. *Table XV for all confounders*)
 - Time-dependent confounders: AOC treatment exposure

In a first model, patient exposure will be modelled according to five categories: exposure to apixaban, dabigatran or rivaroxaban, exposure to VKA or unexposed patients. In a second model, exposure to DOACs will be integrated instead of exposure to apixaban, dabigatran or rivaroxaban. For both models, the reference for comparison will be VKA exposure.

Same models will be performed on AF incident patients with a high thromboembolic risk (if modified CHAD₂DS₂VASC score is ≥ 2 for males and ≥ 3 females). Patient exposure will be modelled according to three categories: exposure to DOAC (Apixaban, Dabigatran or Rivaroxaban), exposure to VKA or unexposed patients. The reference for comparison will also be VKA exposure.

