	Age in years	xx.x	xx.x	xx.x	xx.x	xx.x	xx.x	xx.x (xx.x)	xx.x (xx.x)	xx.x (xx.x)		
Mean (std)	(xx.x)	(xx.x)	(xx.x)	(xx.x)	xx.x (xx.x)	(xx.x)	(xx.x)	xx.x (xx.x)	xx.x (xx.x)	xx.x (xx.x)		
Median	xx.x	xx.x	xx.x	xx.x	xx.x	xx.x	xx.x	xx.x	xx.x	xx.x		
Q1 - Q3	xx.x –	xx.x –	xx.x –	xx.x –	xx.x – xx.x	xx.x	xx.x	xx.x – xx.x	xx.x – xx.x	xx.x – xx.x		
Min - Max	xx.x	xx.x	xx.x	xx.x	xx.x – xx.x	xx.x	xx.x	xx.x – xx.x	xx.x – xx.x	xx.x – xx.x		
Age group: n (%)	xx.x	xx.x	xx.x	xx.x	xx.x (xx.x)	xx.x	xx.x	xx.x (xx.x)	xx.x (xx.x)	xx.x (xx.x)		
<80 years	(xx.x)	(xx.x)	(xx.x)	(xx.x)	(xx.x)	(xx.x)	(xx.x)	(xx.x)	(xx.x)	(xx.x)		
80-90 years	(xx.x)	(xx.x)	(xx.x)	(xx.x)	(xx.x)	(xx.x)	(xx.x)	(xx.x)	(xx.x)	(xx.x)		
>90 years	(xx.x)	(xx.x)	(xx.x)	(xx.x)	(xx.x)	(xx.x)	(xx.x)	(xx.x)	(xx.x)	(xx.x)		
Sex: n (%)	xx.x	xx.x	xx.x	xx.x	xx.x (xx.x)	xx.x	xx.x	xx.x (xx.x)	xx.x (xx.x)	xx.x (xx.x)		
Female	(xx.x)	(xx.x)	(xx.x)	(xx.x)	(xx.x)	(xx.x)	(xx.x)	(xx.x)	(xx.x)	(xx.x)		

	Exposed to OAC				Total exposed to OAC			Unexposed to OAC			Total unexposed To OAC	
	2016 (N=XXX)	2017 (N=XXX)	2018 (N=XXX)	2019 (N=XXX)	2016-2019 (N=XXX)	2016 (N=XXX)	2017 (N=XXX)	2018 (N=XXX)	2019 (N=XXX)	2016-2019 (N=XXX)	2016-2019 (N=XXX)	
	xx.x	xx.x	xx.x	xx.x	xx.x (xx.x)	xx.x	xx.x	xx.x (xx.x)	xx.x (xx.x)	xx.x (xx.x)	xx.x (xx.x)	
Male	(xx.x)	(xx.x)	(xx.x)	(xx.x)		(xx.x)	(xx.x)					
Exposed to DOACs, at index date: n (%)	xx.x	xx.x	xx.x	xx.x	xx.x (xx.x)	xx.x	xx.x	xx.x (xx.x)	xx.x (xx.x)	xx.x (xx.x)	xx.x (xx.x)	
	(xx.x)	(xx.x)	(xx.x)	(xx.x)		(xx.x)	(xx.x)					
Apixaban	xx.x	xx.x	xx.x	xx.x	xx.x (xx.x)	xx.x	xx.x	xx.x (xx.x)	xx.x (xx.x)	xx.x (xx.x)	xx.x (xx.x)	
Dabigatran	(xx.x)	(xx.x)	(xx.x)	(xx.x)		(xx.x)	(xx.x)					
	xx.x	xx.x	xx.x	xx.x	xx.x (xx.x)	xx.x	xx.x	xx.x (xx.x)	xx.x (xx.x)	xx.x (xx.x)	xx.x (xx.x)	
Rivaroxaban	(xx.x)	(xx.x)	(xx.x)	(xx.x)		(xx.x)	(xx.x)					
Exposed to VKA, at index date: n (%)	xx.x	xx.x	xx.x	xx.x	xx.x (xx.x)	xx.x	xx.x	xx.x (xx.x)	xx.x (xx.x)	xx.x (xx.x)	xx.x (xx.x)	
	(xx.x)	(xx.x)	(xx.x)	(xx.x)		(xx.x)	(xx.x)					
Contraindications to OAC, at index date: n (%)	xx.x	xx.x	xx.x	xx.x	xx.x (xx.x)	xx.x	xx.x	xx.x	xx.x (xx.x)			
	(xx.x)	(xx.x)	(xx.x)	(xx.x)		(xx.x)	(xx.x)	(xx.x)	(xx.x)			
Complimentary universal health care (CMU-c): n (%)	xx.x	xx.x	xx.x	xx.x	xx.x (xx.x)	xx.x	xx.x	xx.x (xx.x)	xx.x (xx.x)	xx.x (xx.x)	xx.x (xx.x)	
	(xx.x)	(xx.x)	(xx.x)	(xx.x)		(xx.x)	(xx.x)	(xx.x)	(xx.x)			
Yes	xx.x	xx.x	xx.x	xx.x	xx.x (xx.x)	xx.x	xx.x	xx.x (xx.x)	xx.x (xx.x)	xx.x (xx.x)	xx.x (xx.x)	

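### Contraindication to OAC: the exclusion lists disagree, and the flag the SAP derives is left out of the exposed-versus-unexposed models, so residual confounding remains

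*Protocol*

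**What the plan says.** Protocol 3.2.1 gives two accounts of who is excluded. The detailed list opens with "The exclusion criteria for the AF population correspond to those applied in the NACORA and NAXOS studies and are" and then names valve disease or surgery and OAC taken for another indication. The summary table that follows adds "History of valvular pathology and contraindications to OAC treatment", without codes or a definition, above a note that further exclusions will be discussed with the Scientific Committee.

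SAP 9.2.3.2 says "Patients will be excluded from the study if they meet any exclusion criteria" and lists two items: valve disease or surgery, and "Standard SNDS exclusion criteria (e.g. unicity of identifier not guaranteed, twins, aberrant demographic data, beneficiaries from Mayotte overseas French territory". SAP 9.4.1 says that "all the variables representing the exclusion criteria will be derived for each AF patients"; Table IV then holds only those same two items.

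SAP 9.4.3.1 (Table XII) nevertheless derives a contraindication variable, set to Yes "if the patient presents at least one contraindication to OAC among the followings": dialysis, blood diseases, immune disorders, recent bleeding ulcer, and cirrhosis or liver failure. In the shells it appears as a row such as "Contraindications to OAC, at index date: n" in Table A4, and again in Table A7.

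SAP 9.7.4.2 specifies "The adjusted hazard ratio on potential confounders including patient" characteristics and refers to Table XV for the full set. The flag is in neither place.

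**The concern.** A contraindication makes it less likely that a patient receives an OAC. The background sections of both documents link it mainly to a major risk of bleeding, so it plausibly bears on exposure and on at least one outcome. A variable of that kind belongs either in the eligibility criteria or in the adjustment set of an exposed-versus-unexposed comparison. The summary table puts it in the first; the SAP puts it in neither.

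At stake are the hazard ratios for unexposed patients against VKA in Tables A10 and A11. If contraindicated patients are over-represented in unexposed time, those ratios are pushed upward for outcomes that a contraindication predicts. Both documents expect about a million or more exposed patients, so confidence intervals should be narrow and even a modest bias could look like a precise effect. The limitations section does not mention the problem.

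**Working it through.** **Step 1. Eligibility.** Contraindication is named in one place (Protocol 3.2.1, summary table). It is absent from the detailed list in Protocol 3.2.1, from SAP 9.2.3.2 and from SAP Table IV. Tables A4 and A7 have rows counting flagged patients, and A7 describes the population of the Cox analyses, so the SAP intends to keep them. I could not see the selection figures (Protocol Figure 1, SAP Figures 2 and A1).

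**Step 2. Use of the flag.** It is absent from Table XV, the text of 9.7.4.2, the footnotes to Tables A10 and A11, the sub-populations (9.2.3.4), the stratification groups (9.2.3.5) and all five sensitivity analyses (9.7.6). The only restricted Cox run is on high thromboembolic risk. The primary event rates are standardised on age alone (9.7.3.1).

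**Step 3. What the planned covariates already cover.** Table XV includes HAS-BLED and ACCI; 9.7.4.2 adds history of major bleeding.

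| Flag component | HAS-BLED | ACCI | History of major bleeding |
|---|---|---|---|
| Dialysis | in the renal item | in the renal item | no |
| Liver (K70.4, K71.1, K72.1, K72.9, K76.5–K76.7) | within K70–K77 | all seven codes, moderate-to-severe liver item | no |
| Bleeding ulcer (K254, K264, K274, K284) | all four, primary diagnosis only | ulcer item carries 0 points | all four, main or related diagnosis |
| Blood diseases (D55–D77) | D62, D683, D698, D699 only, primary diagnosis | no | D62 only |
| Immune disorders (D80–D89) | no | no | no |

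The flag accepts any diagnosis position for ulcer bleeding and blood disease, so cases coded only as associated diagnoses reach the flag but not the bleeding proxies. HAS-BLED also gives dialysis the same single point as hypertension or age over 65. The footnotes to Tables A10 and A11 list neither HAS-BLED nor ACCI, so it is unclear whether this partial control will be applied. The frailty indicator in Table XV rests on a code list the SAP does not print, so its overlap cannot be judged.

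**Step 4. Scale.** The plan gives no figure to reproduce. For a single binary confounder, the factor by which the unexposed hazard ratio is inflated is approximately

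B = [1 + p1(RR − 1)] / [1 + p0(RR − 1)],

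where p1 and p0 are the flagged proportions in unexposed and exposed patients and RR is the hazard ratio for flagged against unflagged. All inputs are assumptions: p1 15–30%, p0 8–10%, RR 2–3.

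| p1 | p0 | RR = 2 | RR = 3 |
|---|---|---|---|
| 0.15 | 0.10 | 1.15/1.10 = 1.05 | 1.30/1.20 = 1.08 |
| 0.15 | 0.08 | 1.15/1.08 = 1.06 | 1.30/1.16 = 1.12 |
| 0.30 | 0.10 | 1.30/1.10 = 1.18 | 1.60/1.20 = 1.33 |
| 0.30 | 0.08 | 1.30/1.08 = 1.20 | 1.60/1.16 = 1.38 |

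B rises with p1 and with RR and falls with p0, so the corners bound the range: 1.05 to 1.38. With other assumed inputs it runs from 1.025/1.01 = 1.015 (5% against 2%, RR 1.5) to 1.60/1.10 = 1.455 (30% against 5%, RR 3). None of these figures allows for the proxies in step 3.

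**The case against.** A reader might infer that the protocol plainly excludes contraindicated patients and that the SAP breaks with it. The documents do not support that. The detailed exclusion list omits the item, and the SAP agrees with that list on this point. The protocol contradicts itself, and a cohort without flagged patients cannot simply be called the protocol population.

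A reader might also infer that the models have no control for contraindication. That is too strong: three of the five components overlap with HAS-BLED, ACCI or history of major bleeding. What remains uncovered is the immune block, most of the blood-disease block, and ulcer bleeding coded only as an associated diagnosis.

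The flag itself is broad. It takes whole ICD-10 blocks, and Table A4 provides for flagged patients among the exposed, so a uniform two- to threefold hazard is doubtful. The argument is also stronger for bleeding and death than for stroke. Finally, exposure is time-dependent and unexposed time includes time after stopping an OAC (Table VII), so index-date prevalences are only rough stand-ins for shares of person-time.

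These objections limit the size of the problem. They do not explain why a variable the SAP already derives is kept out of every comparison, or which exclusion list governs.

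**Conclusion.** The point holds as an unreconciled population definition together with an incomplete adjustment set. The SAP keeps contraindicated patients without documenting why, and its models control for contraindication only in part, through proxies that its own table footnotes omit. Residual confounding is left in the unexposed-versus-VKA hazard ratios.

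Its size cannot be derived from the documents. The 1.05 to 1.38 range depends wholly on assumed prevalences and an assumed hazard ratio, and applies before any proxy control. It should not be read as the bias in the adjusted hazard ratio, which is probably smaller. It is worth correcting because the remedy is cheap, but it does not by itself invalidate objective 3.

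**What to change.** 1. Reconcile the two exclusion lists in Protocol 3.2.1 with SAP 9.2.3.2 and Table IV, and record which population applies and why.
2. Add the contraindication flag to Table XV, the covariate text of 9.7.4.2 and the footnotes to Tables A10 and A11. Align those footnotes with Table XV, including HAS-BLED and ACCI.
3. Add a sensitivity run of objective 3 without flagged patients to 9.7.6.
4. If flagged patients stay in the cohort, show them as a separate row in the descriptive event rates (Table A2), which preserves the aim of describing all unexposed AF patients.

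The cost is one covariate that is already derived, one extra run and some text. The restricted run has a smaller unexposed group. A flag fixed at the index date does not capture contraindications that arise during follow-up, so this reduces the confounding without removing it; the limitations section should say so.

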3.2.2. Subpopulations

To meet the objectives of the SIFNOS study, different subpopulations will be split in:

- Elderly AF patients stratified on age-group (≥ 80 years old)
- AF patients having a history of coronary arterial disease (CAD),
- AF frail patients
- AF patients having an active cancer
- AF patients reported with previous stroke.

